
 • To assess whether 80 mg ixekizumab Q2W is superior to placebo at Week 12 in the treatment of patients with moderate to severe genital psoriasis as measured by: 
 ○ GPSIS, Impact of Sexual Activity on Genital Psoriasis Symptoms Subscale for patients who reported as being sexually active at baseline (score of “0” on GPSIS Question 1) ○ Sexual Frequency Questionnaire (SFQ) item 1 ○ Comprehensive Assessment of the Psoriasis Patient (CAPP) Genital sub-index ○ Touch Avoidance NRS ○ Short Form 36 Question Health Survey (SF-36) individual domain scores 	
 • To assess whether 80 mg ixekizumab Q2W is superior to placebo at Week 12 in the treatment of patients with moderate to severe genital psoriasis as measured by: 
 ○ The proportion of patients whose degree of worsening is very low or none at all, or low, GPSIS Impact of Sexual Activity on Genital Psoriasis Symptoms Subscale score of 1 or 2, at Week 12. This will be calculated for patients who reported a score of “0” on GPSIS Question 1 at baseline and had a baseline score of at least 3 ○ The proportion of patients at each level of SFQ item 1 ○ Mean change from baseline in the total CAPP Genital sub-index score ○ Mean change from baseline in the Touch Avoidance NRS ○ The proportion of patients with at least a 5 point improvement from baseline in individual domain scores

Exploratory Objectives	Exploratory Endpoints

 To explore the impact of ixekizumab versus placebo at Week 12 on the change in presence of fissure, ulcer, and/or erosion in the genital area and its association with measures of disease severity and quality of life 	
 The proportion of patients with presence of genital fissure, ulcer, and/or erosion and the association of presence with measures of sPGA of Genitalia (0,1) response and quality of life (SF-36 mental component summary [MCS], Dermatology Life Quality Index [DLQI], GPSIS Subscales, and SFQ items) in the subgroup of patients with fissure, ulcer, and/or erosion

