Psoriasis on inframammary fold	Proportion of patients with absence of psoriasis on inframammary fold	ITT Population – Patients with presence of psoriasis on inframammary fold at baseline	Week 12 and other post-baseline visits	Fisher’s exact test using NRI	Exploratory	Primary ^e
sPGA of Genitalia and genital fissure/erosion/ulcer	Proportions of patients with absence of genital fissure, compared between two groups of patients achieving and not achieving sPGA of Genitalia (0,1) ^d	ITT Population – Patients with genital fissure at baseline	Week 12	Fisher’s exact test using NRI	Exploratory	Primary ^e
	Proportions of patients with absence of genital erosion, compared between two groups of patients achieving and not achieving sPGA of Genitalia (0,1) ^d	ITT Population – Patients with genital erosion at baseline	Week 12	Fisher’s exact test using NRI	Exploratory	Primary ^e
	Proportions of patients with absence of genital fissure/erosion/ulcer, compared between two groups of patients achieving and not achieving sPGA of Genitalia (0,1) ^d	ITT Population – Patients with genital fissure, erosion, and/or ulcer at baseline	Week 12	Fisher’s exact test using NRI	Exploratory	Primary ^e

Measure	Variable	Population (Section 6.1.1)	Time Point	Analysis and Imputation Method (Sections 6.1.3 and 6.3)	Objective/ Endpoint Type	Analysis Type
SFQ Item 1 and genital fissure/ erosion/ ulcer	Proportion of patients with SFQ Item 1 score response level, compared between two groups of patients with presence/absence of genital fissure ^d	Intent to Treat Population – Patients with genital fissure at baseline	Week 12	Fisher’s exact test	Exploratory	Primary ^e
	Proportion of patients with SFQ Item 1 score response level, compared between two groups of patients with presence/absence of genital erosion ^d	Intent to Treat Population – Patients with genital erosion at baseline	Week 12	Fisher’s exact test	Exploratory	Primary ^e
	Proportion of patients with SFQ Item 1 score response level, compared between two groups of patients with presence/absence of genital fissure, erosion, and /or ulcer ^d	Intent to Treat Population – Patients with genital fissure, erosion, and/or ulcer at baseline	Week 12	Fisher’s exact test	Exploratory	Primary ^e

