SFQ Item 1 and psoriasis in perianal/ gluteal cleft area	Proportion of patients with SFQ Item 1 score response level, compared between two groups of patients with	Intent to Treat Population – Patients with psoriasis in perianal and/or gluteal cleft area at baseline	Week 12	Fisher’s exact test	Exploratory	Primary ^e

Measure	Variable	Population (Section 6.1.1)	Time Point	Analysis and Imputation Method (Sections 6.1.3 and 6.3)	Objective/Endpoint Type	Analysis Type
	presence/absence of psoriasis in perianal /gluteal cleft area ^d					
SFQ Item 1 and facial psoriasis	Proportion of patients with SFQ Item 1 score response level, compared between two groups of patients with presence/absence of facial psoriasis ^d	Intent to Treat Population – Patients with facial psoriasis at baseline	Week 12	Fisher’s exact test	Exploratory	Primary ^c
SFQ Item 2 and genital fissure/ erosion/ ulcer	Proportion of patients with SFQ Item 2 score of 0 or 1, compared between two groups of patients with presence/ absence of genital fissure ^d	Intent to Treat Population – Patients with SFQ Item 2 score ≥ 2 and with genital fissure at baseline	Week 12	Fisher’s exact test using NRI	Exploratory	Primary ^c
	Proportion of patients with SFQ Item 2 score of 0 or 1, compared between two groups of patients with presence/absence of genital erosion ^d	Intent to Treat Population – Patients with SFQ Item 2 score ≥ 2 and with genital erosion at baseline	Week 12	Fisher’s exact test using NRI	Exploratory	Primary ^c
	Proportion of patients with SFQ Item 2 score of 0 or 1, compared between two	Intent to Treat Population – Patients with SFQ Item 2 score ≥ 2 and	Week 12	Fisher’s exact test using NRI	Exploratory	Primary ^c

Measure	Variable	Population (Section 6.1.1)	Time Point	Analysis and Imputation Method (Sections 6.1.3 and 6.3)	Objective/ Endpoint Type	Analysis Type
	groups of patients with presence/absence of genital fissure, erosion, and /or ulcer ^d	with genital fissure, erosion, and/or ulcer at baseline				
SFQ Item 2 and psoriasis in perianal/gluteal cleft area	Proportion of patients with SFQ Item 2 score of 0 or 1, compared between two groups of patients with presence/absence of psoriasis in perianal/gluteal cleft area ^d	Intent to Treat Population – Patients with SFQ Item 2 score ≥ 2 and psoriasis in perianal and/or gluteal cleft area at baseline	Week 12	Fisher’s exact test using NRI	Exploratory	Primary ^e

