GPSIS Impact Subscale and genital fissure/erosion/ulcer	Proportion of patients with a subscale score of 1 or 2, compared between two groups of patients with presence/absence of genital fissure ^d	ITT population – Patients with GPSIS Impact Subscale Score ≥ 3 and genital fissure at baseline	Week 12	Fisher’s exact test using NRI	Exploratory	Primary ^e
	Proportion of patients with a subscale score of 1 or 2, compared between two groups of patients with presence/absence of genital erosion ^d	ITT population – Patients with GPSIS Impact Subscale Score ≥ 3 and genital erosion at baseline	Week 12	Fisher’s exact test using NRI	Exploratory	Primary ^e
	Proportion of patients with a subscale score of 1 or 2, compared between two groups of patients with presence/absence of genital fissure/erosion/ulcer ^d	ITT population – Patients with GPSIS Impact Subscale Score ≥ 3 and genital fissure, erosion, and/or ulcer at baseline	Week 12	Fisher’s exact test using NRI	Exploratory	Primary ^e

Measure	Variable	Population (Section 6.1.1)	Time Point	Analysis and Imputation Method (Sections 6.1.3 and 6.3)	Objective/ Endpoint Type	Analysis Type
GPSIS Impact Subscale and psoriasis in perianal/gluteal cleft area	Proportion of patients with a subscale score of 1 or 2, compared between two groups of patients with presence/absence of psoriasis in perianal/gluteal cleft area ^d	ITT population – Patients with GPSIS Impact Subscale Score ≥ 3 and psoriasis in perianal and/or gluteal cleft area at baseline	Week 12	Fisher’s exact test using NRI	Exploratory	Primary ^e
DLQI and genital fissure/erosion/ulcer	Proportion of patients with DLQI (0,1), compared between two groups of patients with presence/absence of genital fissure ^d	Intent to Treat Population – Patients with genital fissure at baseline	Week 12	Fisher’s exact test using NRI	Exploratory	Primary ^e
	Proportion of patients with SFQ Item 2 score of 0, compared between two groups of patients with presence/absence of genital erosion ^d	Intent to Treat Population – Patients with genital erosion at baseline	Week 12	Fisher’s exact test using NRI	Exploratory	Primary ^e
	Proportion of patients with SFQ Item 2 score of 0, compared between two groups of patients with presence/absence of genital fissure, erosion, and /or	Intent to Treat Population – Patients with genital fissure, erosion, and/or ulcer at baseline	Week 12	Fisher’s exact test using NRI	Exploratory	Primary ^e

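### Two exploratory rows in the DLQI-by-genital-lesion block of SAP Table RHBQ.6.5 name SFQ Item 2 score of 0 where DLQI (0,1) is evidently meant

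*SAP*

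**What the plan says.** SAP Section 4.3 lists, as an exploratory endpoint, the association of genital lesions with several quality-of-life measures, among them "Dermatology Life Quality Index [DLQI], GPSIS Subscales, and SFQ items) in the subgroup of patients with fissure, ulcer, and/or erosion". Protocol Table RHBQ.3.1 has the corresponding endpoint, and the SAP revision history records that these Week 12 association analyses, DLQI included, were added in Version 2.

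Section 6.10 makes Table RHBQ.6.5 the place where variable, population, time point and method are fixed. In its block for DLQI and genital lesions:

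- The fissure row reads "Proportion of patients with DLQI (0,1), compared between two groups of patients with presence/absence of genital fissure".
- The erosion row reads "Proportion of patients with SFQ Item 2 score of 0, compared between two groups of patients with presence/absence of genital erosion", in the population "Intent to Treat Population – Patients with genital erosion at baseline".
- The composite row begins "Proportion of patients with SFQ Item 2 score of 0, compared between two groups of patients with presence/absence of genital fissure, erosion" and goes on to ulcer. Its population is likewise defined by baseline lesions only.

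SFQ Item 2 has its own lesion block earlier in the same table. The erosion row there reads "Proportion of patients with SFQ Item 2 score of 0 or 1, compared between two groups of patients with presence/absence of genital erosion", and its population is limited to "Patients with SFQ Item 2 score ≥ 2 and with genital erosion at baseline".

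**The concern.** A block labelled DLQI changes instrument after its first row. The table is the operative analysis specification, so the two variable cells cannot be passed over as background text.

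Two things would follow from programming them literally. First, the DLQI association in the combined lesion subgroup, which is the subgroup Section 4.3 names, would not be produced, and neither would the erosion row that the block label leads one to expect. Second, SFQ Item 2 would be reported twice against erosion and twice against the composite, with different responder cut-offs and different denominators and no explanation of the difference.

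**Working it through.** No figure in the plan is at issue, so the check is a row-by-row reading of Table RHBQ.6.5.

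**1. The DLQI-association rows.**

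| Row | Variable named | Fits a DLQI label? |
|---|---|---|
| Genital fissure | DLQI (0,1) | Yes |
| Genital erosion | SFQ Item 2 = 0 | No |
| Fissure, erosion and/or ulcer | SFQ Item 2 = 0 | No |
| Perianal/gluteal cleft | DLQI (0,1) | Yes |
| Facial | DLQI (0,1) | Yes |

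Within the lesion block, 2 of 3 rows do not fit. Across all DLQI-association rows (3 + 1 + 1 = 5), 2 do not fit and 3 do.

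**2. Whether another row supplies the missing analyses.** None does. No other row of the table gives DLQI (0,1) by erosion or by the composite lesion variable.

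**3. Whether changing variable within a block is a pattern of the table.** It is not. The other quality-of-life lesion blocks (SFQ Item 1, SFQ Item 2, GPSIS Avoidance, GPSIS Impact, SF-36 MCS) each keep one variable across their three rows. The SFQ Item 1 erosion row, for example, reads "Proportion of patients with SFQ Item 1 score response level, compared between two groups of patients with presence/absence of genital erosion", and its two sibling rows use the same variable.

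**4. Which cell is wrong, variable or population.** All five SFQ Item 2 association rows (3 lesion + 1 perianal/gluteal + 1 facial) restrict the population to a baseline Item 2 score of at least 2. The two doubtful rows carry no such restriction, and neither does the correct DLQI fissure row. The population cells therefore fit the DLQI, and the variable cells are the ones out of place. Table RHBQ.6.4 agrees: it derives DLQI (0,1) and SFQ Item 2 of 0 or 1, but has no derived variable for Item 2 equal to 0.

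**5. What literal programming would do to SFQ Item 2.** The item runs from 0 to 4.

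- SFQ Item 2 block: baseline 2 to 4, response 0 or 1. Every responder has improved by at least 2 − 1 = 1 point.
- The two stray rows: any baseline score, response 0. A patient at 0 at baseline and at Week 12 counts as a responder with no change. A patient who goes from 2 or more to 1 is a responder in the SFQ block and a non-responder here.

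The number of Item 2 association rows would rise from 5 to 5 + 2 = 7, with two conflicting versions each for erosion and for the composite.

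**The case against.** The strongest reply is that the intention is plain. The label, the first row, the neighbouring DLQI blocks, the population cells, Section 4.3 and the revision history all say DLQI, so a competent programmer would query the cells, and a separate programming specification that we cannot see may already resolve them. That stands as a reason to give the point little weight. It does not remove the defect, because whoever notices must choose between label and cell, and the choice should be recorded in the plan.

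A reader might infer more than the documents support, in four ways:

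- *That the planned DLQI analyses as a whole are lost.* They are not. The fissure, perianal/gluteal and facial rows are correct, and the treatment comparisons of DLQI total score, DLQI (0,1) and Item 9 are untouched.
- *That a stated objective is missed for both rows.* Section 4.3 states the association for the combined lesion subgroup only. The composite row conflicts with a stated endpoint. The erosion row conflicts with its block label and the table's pattern.
- *That a third SFQ definition appears.* The count reaches three only by including Item 1, a different item with no cut-off. For Item 2, a score of 0 is the second definition within the SAP, and it is also the threshold in the protocol's third major secondary endpoint.
- *That score 0 is therefore a deliberate return to the protocol's threshold.* Nothing in the SAP says so, and a deliberate SFQ analysis would not sit under a DLQI label beside a complete SFQ Item 2 block.

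**Conclusion.** Wrong as written, and minor. Two exploratory variable cells in Table RHBQ.6.5 name the wrong instrument. Taken literally, one association planned in Section 4.3 (DLQI by the composite lesion variable) and one implied by the block label (DLQI by erosion) would be missing, and two unintended SFQ Item 2 comparisons would be added.

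The rows are labelled exploratory, are pooled over treatment arms under the table's footnote d, and lie outside the multiplicity procedure of SAP Section 6.4. No primary, secondary or safety result is affected.

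That DLQI (0,1) was intended is an inference from the surrounding cells, though every one of them points the same way. That the cause was copy-paste is only probable. The practical consequence assumes the table is programmed literally.

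**What to change.** In the erosion row and the composite row of the DLQI-by-genital-lesion block, replace SFQ Item 2 score of 0 with DLQI (0,1). The population, time point and method cells can stay as they are.

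The cost is two table cells, with no new data, derivation or analysis method, since DLQI (0,1) is already derived in Table RHBQ.6.4. If the SAP is not to be reissued, the correction can be recorded with its reason in the clinical study report, as protocol Section 9.2 provides for changes that do not alter a principal feature. The programming specification should be checked for the same slip.

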
 To explore the impact of ixekizumab versus placebo at Week 12 on the change in presence of psoriasis in perianal/gluteal cleft area (as indicated by the investigator in the case report form) and its association with measures of quality of life 	
 The proportion of patients with presence of perianal/gluteal cleft psoriasis and the association of presence with measures of quality of life (SF-36 MCS, DLQI, GPSIS Subscales, and SFQ items) in the subgroup of patients with psoriasis located in perianal area and/or gluteal cleft area

 To explore the impact of ixekizumab versus placebo at Week 12 on the change in presence of psoriasis on the face and its association with measures of quality of life 	
 The proportion of patients with presence of facial psoriasis and the association of presence with measures of quality of life (SF-36 MCS, DLQI, and SFQ items) in the subgroup of patients with psoriasis located on the face

 To explore long-term impact of ixekizumab on symptoms and quality of life through Week 52 	
 The change over time through Week 52 in DLQI, SF-36 MCS, GPSS items, GPSIS Subscales, and SFQ items

 To assess the psychometric properties (including reliability, validity, and responsiveness) of the GPSS, GPSIS, SFQ, and sPGA of Genitalia 	
 Test-retest reliability, construct validity, and responsiveness will be assessed by Intra-class Correlation Coefficients (ICCs), Pearson correlation/Spearman rank-based correlation coefficient, and correlations of calculated changes in scores, respectively, or as deemed appropriate

 To measure ixekizumab exposure and assess the relationship between exposure and efficacy, and exposure and immunogenicity 	
 Serum trough concentrations of ixekizumab Model parameters for the exposure-response relationship between ixekizumab serum trough concentrations and efficacy endpoints Ixekizumab serum trough concentrations associated with ADA titer subgroups

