Measure	Variable	Population (Section 6.1.1)	Time Point	Analysis and Imputation Method (Sections 6.1.3 and 6.3)	Objective/Endpoint Type	Analysis Type
Overall PASI	Change from baseline in Overall PASI score	ITT Population: Patients with BSA \geq 10%	Week 12 and other post-baseline visits	MMRM	Exploratory	Primary
	Percentage Improvement from baseline in Overall PASI score	ITT Population: Patients with BSA \geq 10%	Week 12 and other post-baseline visits	MMRM	Exploratory	Primary
	PASI 75	ITT Population: Patients with BSA \geq 10%	Week 12 and other post-baseline visits	Logistic regression analysis using NRI	Exploratory	Primary
			Week 12 and other post-baseline visits	Fisher’s exact test using NRI		Secondary
	PASI 90	ITT Population: Patients with BSA \geq 10%	Week 12 and other post-baseline visits	Logistic regression analysis using NRI	Exploratory	Primary
			Week 12 and other post-baseline visits	Fisher’s exact test using NRI		Secondary
	PASI 100	ITT Population: Patients with BSA \geq 10%	Week 12 and other post-baseline visits	Logistic regression analysis using NRI	Exploratory	Primary
			Week 12 and other post-baseline visits	Fisher’s exact test using NRI		Secondary

Measure	Variable	Population (Section 6.1.1)	Time Point	Analysis and Imputation Method (Sections 6.1.3 and 6.3)	Objective/ Endpoint Type	Analysis Type
CAPP	Change from baseline in CAPP genital sub-index total score	ITT Population	Week 12 and other post-baseline visits	MMRM	Exploratory	Primary
Touch Avoidance NRS	Change from baseline in Touch Avoidance NRS score	ITT Population	Week 12 and other post-baseline visits	MMRM	Exploratory	Primary
Fissure, ulcer, and/or erosion in genital area	Proportion of patients with absence of fissure	ITT Population – Patients with presence of fissure	Week 12 and other post-baseline visits	Fisher’s exact test using NRI	Exploratory	Primary ^c
	Proportion of patients with absence of fissure/erosion/ulcer	ITT Population – Patients with presence of fissure, erosion, and/or ulcer at baseline	Week 12 and other post-baseline visits	Fisher’s exact test using NRI	Exploratory	Primary ^c
	Proportion of patients with absence of erosion	ITT Population – Patients with presence of erosion at baseline	Week 12 and other post-baseline visits	Fisher’s exact test using NRI	Exploratory	Primary ^c

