SF-36 MCS and facial psoriasis	Proportion of patients with SF-36 MCS ≥ 2.5 improvement, compared between two groups of patients with presence/absence of facial psoriasis ^d	Intent to Treat Population – Patients with facial psoriasis at baseline	Week 12	Fisher’s exact test using NRI	Exploratory	Primary ^e

- a Patients should complete the scales in the following order: 1. GPSS, 2. GPSIS, and 3. SFQ. An e-diary will be used to collect GPSS daily, GPSIS and SFQ weekly, up to Week 12 (Visit 7); thereafter, patients will answer these questions only at scheduled study visits. At Week 12 (Visit 7), patients will complete these scales on site before completion of any other assessments.
- b The scores at each post-baseline visit for GPSS, GPSIS and SFQ, in the Blinded Treatment Period and Open-Label Treatment Period, are defined in Table.RHBQ.6.4.
- c The scores at each calendar week in the Blinded Treatment Period, for GPSS, GPSIS and SFQ, are defined in Table.RHBQ.6.4.
- d The variables are derived based on all patients in the analysis population, not for placebo or ixekizumab treated patients separately.
- e The Primary Method for this analysis is the Fisher's exact test instead of the logistic regression model.

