Known-group validity is the extent to which scores from an instrument are different for groups of participants that differ on a relevant clinical or other indicator. Determining known-group validity involves evaluating an instrument in relation to clinical measures of disease status (Stewart et al. 1992; Hays and Revicki 2005). Known-groups validity will be assessed at baseline and Week 12 for: 1) GPSS individual items and total score, 2) GPSIS subscales, 3) SFQ item 2, and 4) sPGA of Genitalia by disease severity. Groups will be defined using several different criteria: 1) using DLQI score categories (score categories: 2-10, 11-20, 21-30); and 2) using PatGA-Genitalia scores (score categories: 0-1, 2-3, 4-5). Additionally, for exploratory purposes, known-groups validity of the SFQ item 2 will be assessed at baseline-and Week 12 using the DLQI sexual difficulties item to define subgroups of patients. Mean scores on the individual items/subscale/total score will be compared for each subgroup using ANCOVA at baseline, and Week 12 controlling for age, sex, and baseline BSA (<10% vs ≥10%).

When the sample size in a subgroup is less than 10% of the analysis population, the subgroup will be repeatedly collapsed with the adjunct subgroups until the sample size in the collapsed subgroup is greater than 10% of the analysis population.

6.20.1.2.5.4. Responsiveness

Responsiveness refers to the extent to which the instrument can detect changes in patients known to have changed in clinical status (Hays and Revicki 2005). The responsiveness of the 1) GPSS item and total score, 2) GPSS subscales, 3) SFQ Item #2, and 4) sPGA of Genitalia will be determined by comparing changes in item/total scores with the changes in selected clinical and health status measures.

The following variables and time points will be used for these analyses:

- **PatGA-Genitalia:** The change scores of the GPSS item and total score from baseline to Week 12 will be correlated with changes in the PatGA-Genitalia at these time points. The change scores of the individual items and GPSS total score from baseline to Week 12 will also be examined using PatGA-Genitalia as an anchor. The means of GPSS and sPGA of Genitalia scores will be compared for patients reporting ≥ 1 point PatGA-Genitalia Improvement, no change, or ≥ 1 worsening in PatGA-Genitalia using ANCOVA adjusted for age, sex, genital psoriasis duration and baseline scores.

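### The 32 exploratory Week 12 lesion-association tests pool both arms with no stratified or by-arm version, so where ixekizumab improves both variables a significant result does not isolate a lesion-outcome link

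*SAP*

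**What the plan says.** SAP Section 4.3 lists exploratory endpoints on genital fissure, ulcer or erosion, on perianal or gluteal cleft psoriasis, and on facial psoriasis. For genital lesions the endpoint includes "the association of presence with measures of sPGA of Genitalia (0,1) response and quality of life". For perianal or gluteal cleft psoriasis it includes "the association of presence with measures of quality of life (SF-36 MCS, DLQI, GPSIS Subscales, and SFQ items) in the subgroup of patients" with psoriasis at that site.

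Table RHBQ.6.5 (SAP Section 6.10) implements these endpoints in 32 Week 12 rows carrying footnote d. A typical row reads "Proportion of patients with SFQ Item 2 score of 0 or 1, compared between two groups of patients", the groups being defined by presence or absence of the lesion. The three sPGA of Genitalia rows work the other way round and compare lesion absence between responders and non-responders. Every row is exploratory and uses a single Fisher's exact test. Footnote d states the pooling: "The variables are derived based on all patients in the analysis population, not for placebo or ixekizumab treated patients separately". Footnote e makes Fisher's exact test the primary method for these rows in place of logistic regression, so no treatment term enters.

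Separate rows, such as "Proportion of patients with absence of fissure/erosion/ulcer", are not marked with footnote d. They give the arm effect on lesions but do not cross lesion status with an outcome. The efficacy subgroup analyses (SAP Section 6.17.1) cover BSA category, sex, age and region only. SAP Section 6.20 leaves room for further exploratory analyses but names no stratified version of these.

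**The concern.** Randomised treatment is a likely common cause of both variables in these rows. The trial is designed to show that ixekizumab improves sPGA of Genitalia, SFQ Item 2, GPSIS avoidance, DLQI and SF-36 outcomes, and its exploratory objectives look for an effect on the lesions. If both effects occur, patients whose lesions have cleared come disproportionately from the ixekizumab arm, and so do patients with good outcomes. The pooled table then shows an association even if, within each arm, clearing the lesion says nothing about the outcome.

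What is at stake is interpretation. A small pooled p-value could be reported as evidence that fissures or perianal disease go with worse quality of life, when it may show only that the drug works on both. The better the trial succeeds, the harder the pooled result is to read.

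**Working it through.** **Row count.** sPGA of Genitalia 3, SFQ Item 1 5, SFQ Item 2 5, GPSIS avoidance 5, GPSIS impact 4, rows headed DLQI 5, SF-36 MCS 5: 3 + 5 + 5 + 5 + 4 + 5 + 5 = 32. Two of the rows headed DLQI (erosion; fissure, erosion and/or ulcer) actually name an SFQ Item 2 score of 0 as the variable. The SFQ Item 1 rows have a three-level outcome ("Proportion of patients with SFQ Item 1 score response level, compared between two groups of patients") and do not mention NRI. The other 32 − 5 = 27 are two-level and specify NRI.

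**Inputs.** The plan gives no lesion prevalence, clearance rate or response rate for these subsets, so there is no figure to reproduce and all rates below are assumed. Arms are equal (1:1 allocation).

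**Pooled odds ratio with no within-arm association and no dropout.** Let L be the probability of lesion absence and R the probability of response in an arm. Summing L·R, L(1−R), (1−L)R and (1−L)(1−R) over the two arms gives the pooled 2×2 table.

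- (a) Absence 70/30%, response 50/10% (ixekizumab/placebo): cells 0.35 + 0.03 = 0.38; 0.35 + 0.27 = 0.62; 0.15 + 0.07 = 0.22; 0.15 + 0.63 = 0.78. OR = (0.38 × 0.78)/(0.62 × 0.22) = 2.17.
- (b) Absence 80/30%, response 60/10%: cells 0.51, 0.59, 0.19, 0.71. OR = (0.51 × 0.71)/(0.59 × 0.19) = 3.23.
- (c) Absence 60/40%, response 40/20%: cells 0.32, 0.68, 0.28, 0.72. OR = (0.32 × 0.72)/(0.68 × 0.28) = 1.21.
- (d) Only the lesion moves, absence 70/30%, response 30% in both arms: cells 0.30, 0.70, 0.30, 0.70. OR = 1.00.

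The within-arm odds ratio is 1 in every case.

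**Rejection at two-sided 0.05 (simulated, no dropout).**

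| Scenario | Pooled Fisher, 10 to 50 per arm | CMH stratified by arm |
|---|---|---|
| (a) | 6% to 38% | about 4% to 5% |
| (b) | 12% to 73% | about 4% to 5% |
| (c) | 2% to 6% | about 5% |
| (d) | 2% to 4% | about 4% to 5% |

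For three-level SFQ Item 1 (absence 70/30%; levels 45/30/25% versus 15/25/60%), the pooled exact test rejects in 7% to 8% of trials at 10 per arm and 26% at 50. Generalised CMH stays below 5%.

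**Dependence on allocation.** With 2:1 randomisation, scenario (a) gives cells 0.73, 0.97, 0.37, 0.93 and OR = (0.73 × 0.93)/(0.97 × 0.37) = 1.89 instead of 2.17. Within either arm it is 1.00. So part of the pooled odds ratio reflects the design.

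**What stratifying does not remove.** Suppose NRI counts a dropout both as lesion not cleared and as non-responder; the SAP does not say how NRI applies to the grouping variable. Dropouts then all fall in one cell. In (a) with 10% dropout on ixekizumab the cells are 0.315, 0.315, 0.135 and 0.135 + 0.10 = 0.235, so the within-arm OR is (0.315 × 0.235)/(0.315 × 0.135) = 1.74. With 20% on placebo they are 0.024, 0.216, 0.056 and 0.504 + 0.20 = 0.704, giving 1.40. Under this assumed 10%/20% dropout, CMH by arm rejects in about 9% to 14% of trials at 20 per arm and 12% to 27% at 50, across (a) to (c) and a case where treatment moves neither variable.

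**The case against.** The strongest reply is that this is a disclosed choice of estimand. Section 4.3 asks about association among patients with the lesion and does not say within arm; footnote d states the pooling openly; and the pooled table does describe that population. That stands, so the pooled table should be kept. It does not settle the matter. A quantity that shifts with the randomisation ratio, and that can arise from two treatment effects alone, is a poor basis for saying that lesion presence goes with worse outcomes. Treatment is also the one common cause the trial itself creates and records.

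The size is wholly assumed. The upper rejection rates need about 50 per arm out of 73, whereas each row requires a baseline lesion and many add a second baseline filter, so smaller subsets are plausible. In (a) at 10 per arm the inflation is negligible, and in (c) it is absent or slight at every size. For the sPGA rows, zero within-arm association is also a severe benchmark, because the investigator records the genital lesions and rates genital severity at the same visits. These limits stand and keep the point minor.

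A reader might infer an internal inconsistency. The documents do not support that: the psychometric known-groups comparisons also leave treatment out, "controlling for age, sex, and baseline BSA" only.

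A reader might also infer that a stratified test would isolate the lesion-outcome link. It would not. Confounding by severity remains and, in the 27 NRI rows, so may the association that imputation creates.

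**Conclusion.** The concern holds in a limited form. Each of the 32 rows rests on one pooled Fisher test, with no planned output that crosses lesion status with outcome within an arm. Where ixekizumab improves both variables, a significant pooled result can come from the arm effects alone. The point applies row by row. If treatment moves only one variable and there is no dropout, there is no spurious association.

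The magnitudes rest on assumed rates, on independence within arms and on no dropout; the documents cannot place the trial within the range. They do not support a claim that all 32 tests are invalid or that false positives are assured. Nor is there any effect on the primary or major secondary conclusions, since every row is exploratory and outside the sequential testing. Severity is minor.

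**What to change.** - For the 27 two-level rows, report a CMH test and common odds ratio stratified by randomised treatment, or logistic regression with treatment as a factor. Use a stratified exact version where cells are sparse.
- For the five SFQ Item 1 rows, use a generalised CMH or stratified exact test.
- Show each table by arm and keep the pooled table as descriptive.
- State that stratification removes only the between-arm component, not severity confounding or an association created by NRI. Say how NRI applies to the lesion variable, and show the observed-data version of the 27 NRI rows alongside.
- Reconcile the two rows headed DLQI with the SFQ Item 2 variable they name.

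The cost is SAP table wording and a little programming. The SAP already fits logistic models with treatment for the TE-ADA and subgroup analyses of sPGA of Genitalia. Protocol Section 9.2 lets changes that do not alter a principal feature be described in the CSR, so no protocol amendment is needed.

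Intervals widen somewhat. The asymptotic standard error of the log odds ratio, stratified relative to pooled, is 1.18 in (a), 1.30 in (b) and 1.04 in (c). Power in small subsets is low: at 20 per arm CMH detects a within-arm odds ratio of 3 in about 24% to 31% of trials. Where treatment moves neither variable, stratifying costs almost nothing: for the same odds ratio the stratified exact test and pooled Fisher both reject in about 26% of trials at 20 per arm.
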